- At screening the MRI/CT scans will include brain imaging (MRI preferred) for all patients randomised under CSP version 7.0. Those determined to have brain metastases at baseline or those who had a history of brain metastases will have their brain rescanned (using the same modality as at baseline) at all subsequent tumour assessments until RECIST 1.1-defined PD (including PD). In patients without brain metastases at baseline and without a history of brain metastases, brain scans will be performed only when there is a suspected CNS progression and at the RECIST 1.1-defined extracranial progression. The brain scan is required for all patients at PD by investigator assessment per RECIST 1.1 and should be performed within 4 weeks, but preferably as soon as possible, to allow the assessment of new lesions in the brain.
- ePRO (Electronic devices; LogPads) must be assigned to patients confirmed as eligible for the study, following registration in IWRS after which the device may be taken home by the patient: baseline ePROs must be completed by patients prior to dosing on Cycle 1 Day 1. Screening ePRO assessments offer the opportunity for site staff to set up the device, add the patient, and for the patient to practice reporting ePROs for the first time and make themselves familiar with the device before the baseline assessment at Cycle 1 Day 1. PRO-CTCAE will be administered only in the languages where a linguistically validated version exists. LogPads used for ePRO collection should be returned to site at the nearest visit as soon as the last assessment is completed by patient.
- For patients on the savolitinib 300 mg bid + placebo arm who are eligible for cross over to the savolitinib 300 mg + osimertinib combination arm, the ePRO must be completed after progressive disease is assessed and confirmed by the Investigator, and before crossing over to the combination arm (within 7 days of the final dose of savolitinib + placebo).
- Triplicate ECGs will be required on Cycle 3 Day 1 collected to coincide with collection of blood samples for assessment of PK of osimertinib and savolitinib at this visit.
- Patients will be contacted for survival follow-up every 12 weeks until death, withdrawal of consent or the end of the study ie, at the time of final analysis. Patients should be contacted in the week following the data cut-offs to provide complete survival data. SAEs considered related to study treatment will be collected throughout survival follow-up.

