4.1.2 Crossover

At investigator-assessed PD per RECIST 1.1, treatment allocation will be unblinded and those patients randomised to the savolitinib plus placebo arm will have the opportunity to cross over to the savolitinib plus osimertinib regimen. Patients will be informed of the possibility of crossover to savolitinib plus osimertinib during the initial informed consent process and at the

time of progression on randomised treatment. A separate informed consent form (ICF) for crossover patients must be signed prior to starting crossover treatment.

Patients who cross over must not receive any other anti-cancer therapies between the initial assessment of PD and the addition of osimertinib. Savolitinib treatment should continue uninterrupted during this period. Patients should be crossed over as soon as possible after the assessment of PD and within 28 days of their progression scan.

Patients who cross over will receive study medication once daily in 28-day cycles until objective PD by RECIST 1.1 is assessed by investigator, unacceptable toxicity occurs, consent is withdrawn or another discontinuation criterion is met. As in the treatment allocation/randomisation part of the study, patients may continue to receive treatment with osimertinib plus savolitinib or osimertinib monotherapy (if savolitinib is stopped during cross over because of savolitinib-related toxicity) beyond RECIST 1.1 defined PD as long as they continue to receive clinical benefit, in the opinion of the investigator, and do not meet any of the discontinuation criteria. No other anti-cancer agent is permitted in combination with osimertinib within this study.

If, after the planned futility analysis the savolitinib + placebo arm is declared futile, all patients remaining on savolitinib + placebo will be contacted and asked to return for a discussion of the futility findings and their options for remaining in the savolitinib + placebo arm (as long as, in the opinion of the investigator, they are still receiving clinical benefit and have not reported PD) or crossing over to the savolitinib + osimertinib arm. Patients who cross over must not receive any other intervening anti-cancer therapies before the addition of osimertinib.

All patients who cross over to receive savolitinib + osimertinib (whether based on objective PD by RECIST 1.1 or a declaration of futility of the savolitinib + placebo arm) will follow the scheduled procedures described in [Table 2](#).

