2.2 Analysis Sets

The analysis sets are presented in [Table 2](#).

Patients will be assigned to each of the populations in Table 2 and to the diagnostic populations (centrally confirmed by FISH [FISH5+, FISH10+] and centrally confirmed by IHC [IHC50+, IHC90+]), prior to any analyses being performed. Additional details on diagnostic populations can be found in section [4.1](#).

Table 2 Analysis Sets

Analysis Set	Definition
Target Population Analysis Set (TPAS)	All patients assigned to savolitinib 300 mg bid + osimertinib who have FISH10+ and/or IHC90+ status, have progressed following 1L osimertinib, and have taken ≥ 1 dose of either study drug.
Contribution of Components Analysis Set (CAS)	All patients randomised under CSP version 7.0 with treatment groups assigned in accordance with the randomisation, regardless of the treatment actually received.
Safety Analysis Set (SAF)	All enrolled patients who take ≥ 1 dose of either study drug.
PK Analysis Set	All patients who receive at least 1 dose of savolitinib or osimertinib as per the protocol for whom any post-dose PK data are available and do not violate or deviate from the protocol in ways that would significantly affect the PK analyses will be included in the PK analysis set.
Evaluable for Response	Dosed patients who have measurable disease at baseline. This population will only be used for interim analyses.
Evaluable for Response 2	Dosed patients with measurable disease at baseline who have had the opportunity for 2 on-treatment RECIST scans. This population will only be used for interim analyses.
Safety Analysis Set 2 (SAF2)	All enrolled patients who take ≥ 1 dose of either study drug who have had the opportunity to be treated for 6 weeks. This population will only be used for interim analyses.

CSP Clinical study protocol; FISH Fluorescence in situ hybridisation; IHC immunohistochemistry; PK Pharmacokinetic(s); RECIST Response Evaluation Criteria in Solid Tumor.

If during the study a patient stops one of the two study treatments and continues on monotherapy or a patient crossover to the combo treatment, the data for the patient will continue to be treated as per the initial treatment allocation.

For the Pharmacokinetic [PK] analysis set, where a protocol deviation impacts only part of a patient's data, the affected portion of the patient's PK data will be excluded from PK analysis and summary statistics, and the remaining valid data will be utilised.

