3 DESCRIPTION OF VARIABLES

3.1 General principles

3.1.1 Baseline measurements and change from baseline variables

Baseline for patients allocated/randomised to treatment will be the last assessment of the variable under consideration prior to the intake of the first dose, except for efficacy variables. For efficacy variables, baseline is defined as the last non-missing assessment prior to randomisation (patients enrolled under CSP version 7.0) or last non-missing assessment prior to first dose (patients enrolled prior to CSP version 7.0). For patients who cross over from savolitinib plus placebo to savolitinib plus osimertinib, their data will be cut off for the purposes of any savolitinib plus placebo assessment at the last assessment of the variable under consideration prior to the intake of the first dose of the combination therapy.

If two assessments are equally eligible to assess patient status at baseline (e.g. on the same date prior to first dose with no time recorded to distinguish the assessments), the average should be taken as the baseline value. For non-numeric laboratory tests (i.e. some of the urinalysis parameters) where taking an average is not possible then the best value would be taken as baseline as this is the most conservative. In the scenario where there are two assessments on Day 1, one with time recorded and the other without time recorded, the one with time recorded would be selected as baseline, assuming it could be determined that it occurred prior to first dose. Where safety data are summarised over time, study day will be calculated in relation to date of first treatment. If no value exists before the first dose/administration, then the baseline value will be treated as missing.

Regarding electronic Patient reported outcome [ePRO] questionnaires, the baseline is defined as the non-missing assessment collected at Day 1, as it is assumed it is taken prior to start of the study treatment. If an assessment is missing at Day 1, the prior non-missing assessment will be used as baseline.

In all summaries change from baseline variables will be calculated as the post treatment value minus the

value at baseline. For % change from baseline, calculate:

$$\% \text{ change from baseline} = \frac{(\text{Post baseline value} - \text{Baseline Value})}{\text{Baseline value}} \times 100$$

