4.2.2.9 Exploratory Endpoint – CNS Metastases

4.2.2.9.1 Contribution of Components Analysis Set

The CNS metastases analyses will be produced using the CAS for:

- 300 mg bid (savolitinib) + osimertinib
- 300 mg bid (savolitinib) + placebo

The CNS PFS, CNS ORR and CNS DoR by BICR will be explored to assess the efficacy of savolitinib plus osimertinib and savolitinib plus placebo, respectively, on CNS metastases in patients with CNS metastases at baseline.

The presence/absence of CNS lesions at progression by BICR in patients without CNS metastases at baseline will be presented using descriptive statistics.

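### The rules for patients who cross over conflict on whether a brain scan done after PD counts, so an exploratory CNS endpoint could lose assessments in the placebo arm only

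*Protocol*

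**What the plan says.** **Imaging.** In patients without baseline or past brain metastases, "brain scans will be performed only when there is a suspected CNS progression and at the RECIST 1.1-defined extracranial progression" (Protocol 1.1, Table 1 footnote on tumour imaging; repeated in 8.1.1). For the scan at progression the same footnote states: "The brain scan is required for all patients at PD by investigator assessment per RECIST 1.1 and should be performed within 4 weeks". It adds a preference for early scanning, so that new brain lesions can be picked up.

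**Crossover.** Protocol 4.1.2 unblinds at investigator PD and offers savolitinib + placebo patients the combination: "Patients should be crossed over as soon as possible after the assessment of PD and within 28 days of their progression scan". After crossover for PD, scheduled RECIST imaging is no longer required (Protocol 8.1.1 and Table 2).

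**Cut-off.** For patients crossing over from savolitinib + placebo, SAP 3.1.1 says "their data will be cut off for the purposes of any savolitinib plus placebo assessment at the last assessment of the variable under consideration". Only assessments that precede the first combination dose qualify. Protocol 9.4.1 carries the same rule.

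**Competing rule.** SAP 2.2 covers the case where "a patient crossover to the combo treatment, the data for the patient will continue to be treated as per the initial treatment allocation". It mentions no cut-off.

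**Endpoint.** SAP 4.2.2.9.1, by randomised arm in the CAS: "The presence/absence of CNS lesions at progression by BICR in patients without CNS metastases at baseline will be presented using descriptive statistics". It is listed among the exploratory objectives.

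**The concern.** A patient with no baseline or past brain metastases has no routine on-study brain scan. Unless CNS progression is suspected earlier, the scan at PD is the only post-baseline look at the brain. Its window and the crossover window both run for four weeks from about the same date, and no rule puts the scan first. The Table 1 footnotes do set such an order for the ePRO, which must be completed after PD and before crossing over.

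Read literally, the cut-off removes a brain scan taken after the first combination dose. The last qualifying CNS assessment may then be the negative baseline scan. Combination-arm patients do not cross over, so their equally late scans are kept. This endpoint is the only one listed for the objective on prevention of CNS metastases, and its completeness would depend on the arm.

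**Working it through.** The plan states no figure to reproduce, and the version 7.0 arm sizes are redacted. The check sets the rules side by side and then sizes the loss under stated assumptions.

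**Rules for a brain scan within 4 weeks of PD but after the first combination dose**

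- Combination arm: the case cannot arise, so the scan counts.
- Placebo arm under SAP 3.1.1 and Protocol 9.4.1: the scan falls after the cut-off.
- Placebo arm under SAP 2.2: the scan stays with the randomised arm.

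Two programmers could therefore build different placebo-arm tables, each citing the SAP.

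**Share of scans lost**

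Take day 0 as PD for both windows. Let S be the day of the brain scan, D the day of the first combination dose, f = P(S > D), and c the share of placebo-arm progressors who cross over. Share lost = f × c. Uniform timings and c of 60% to 80% are assumptions.

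| S uniform over days | D uniform over days | f | Lost, c = 60% | Lost, c = 80% |
|---|---|---|---|---|
| 0–28 | 0–28 | 1/2 = 50% | 30% | 40% |
| 0–28 | 7–28 | (28 − 17.5)/28 = 37.5% | 22.5% | 30% |
| 0–7 | 0–28 | (1/28) × 3.5 = 12.5% | 7.5% | 10% |
| 0–14 | 7–28 | (1/21) × 1.75 = 8.3% | 5% | 6.7% |
| 0–7 | 7–28 | 0% | 0% | 0% |

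In rows 3 and 4 the multiplier is the integral of (a − d)/a over the days d on which the dose can precede the scan, where a is the end of the scan window: 7²/(2 × 7) = 3.5 and 7²/(2 × 14) = 1.75.

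A harsher pairing, with prompt crossover on days 7–14 and scans still spread over 28 days, gives f = (28 − 10.5)/28 = 62.5% and a loss of 50% at c = 80%. It is left out of the range because it makes sites quick with one task and slow with the other.

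**Effect on the reported rate, assuming a true placebo-arm rate of 30%**

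- Lost scans read as absent: 0.30 × (1 − 0.05) = 28.5%, down to 0.30 × (1 − 0.40) = 18%.
- Lost scans missing, loss unrelated to CNS status: the expected rate stays at 30% and the denominator shrinks by the share lost.
- Lost scans missing, loss related to CNS status: either direction is possible. If 40% of patients with lesions and 5% of those without lose the scan, the rate is 0.18/(0.18 + 0.665) = 21.3%. With the shares reversed it is 0.285/(0.285 + 0.42) = 40.4%.

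These are ceilings. A CNS lesion that itself triggered PD was imaged before crossover and is kept.

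**The case against.** The strongest reply is that SAP 2.2, with a CAS defined by randomisation whatever treatment was received, already keeps the scan in its arm. The cut-off sentence also sits in a section on baseline and change from baseline. SAP 3.2.1.1.5 accepts that scans contributing to one visit may be done on different dates, so a brain scan prompted by PD could be attributed to the PD visit. All images go to central review in any case.

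Part of this stands. It is not established that the late scan will be discarded, and the image itself is not lost. But the cut-off is the more specific rule, covers any savolitinib + placebo assessment, and appears in both documents. SAP 2.2 is not reconciled with it, and nothing says which visit a late brain scan belongs to.

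The reply on size also stands. The footnote prefers an early scan. Crossover needs documented PD, approval for unblinding (Protocol 6.3), separate consent and a completed ePRO. Prompt scanning could bring the loss to zero.

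A reader might go further and infer that the plan biases the randomised CNS comparison in a known direction and hides an effect of osimertinib. That requires a lost scan to be scored as absent. No section says so, and SAP 3.1.4 says efficacy data are in general not imputed.

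**Conclusion.** The point holds as a conflict between rules that can cost one randomised arm its assessments. Under the cut-off, 0% to about 40% of placebo-arm progressors without baseline or past brain metastases would lose the PD brain scan. That range rests entirely on assumed timings and crossover shares. The sure consequence is less information in one arm. Bias is possible but of unknown direction if lost scans are missing, and the placebo-arm rate is understated only if they are read as absent.

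The scope is narrow: one exploratory, descriptive endpoint. CNS PFS might seem equally exposed, but it concerns patients with CNS metastases at baseline, who have brain imaging at every tumour assessment including PD, so it is less affected. No primary or secondary result depends on this endpoint.

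**What to change.** 1. In SAP 3.1.1 and 4.2.2.9.1, state that a brain scan triggered by PD and done within the 4-week window belongs to the PD assessment, is exempt from the crossover cut-off, and is counted in the randomised arm. Limit this to investigator PD that preceded the first combination dose.
2. Reconcile SAP 2.2 with SAP 3.1.1 and Protocol 9.4.1. Because the Protocol carries the same cut-off, record the change in SAP section 6.
3. Report by arm the number of PD brain scans missing and the number taken after the first combination dose.
4. Reconcile the timing text in Protocol 1.1 and 8.1.1 with that in 4.1.2. The order of scan and crossover is for the sponsor to decide.

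The cost is SAP wording, one extra table row and reconciliation of existing Protocol text; no extra scan is needed. The downside is that some counted scans would follow osimertinib exposure of at most about 4 weeks. A sensitivity summary without those scans would show whether that matters.

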1.2 Synopsis

International Co-ordinating Investigators:

[name],

Samsung Medical Centre Sungkyunkwan University School of Medicine, [name],
Korea

PPD

Massachusetts General Hospital Cancer Centre, [name]

Protocol Title: A Phase II Study Assessing the Efficacy of Osimertinib in Combination with Savolitinib in Patients with EGFRm+ and MET+, Locally Advanced or Metastatic Non-Small Cell Lung Cancer who have Progressed Following Treatment with Osimertinib (The SAVANNAH Study).

Short Title: Osimertinib plus savolitinib in EGFRm+/ MET+ NSCLC following prior osimertinib

Rationale:

Osimertinib (TagrissoTM) is a potent irreversible inhibitor of sensitising epidermal growth factor receptor (EGFR) mutations and T790M mutation-positive forms of EGFR. Osimertinib acts on tumours by blocking abnormal EGFR-mediated signalling, leading to profound tumour growth inhibition in EGFR mutation bearing non-small cell lung cancer (NSCLC). However, resistance to osimertinib is an emerging and important unmet clinical problem. One of the major mechanisms for resistance is amplification and/or overexpression of the hepatocyte growth factor (HGF) receptor, mesenchymal epithelial transition factor (MET) tyrosine kinase, which activates downstream intracellular signalling independent of EGFR. Presently, there is no approved therapy specifically indicated for the treatment of patients with tumours positive for MET-amplification and/or overexpression, and there is no established standard of care specifically for patients who have developed MET-driven resistance after prior EGFR-tyrosine kinase inhibitor (TKI) therapy (including osimertinib).

Savolitinib is a potent and selective MET-TKI which has been shown to inhibit cell growth against tumours with MET-amplification in the absence of HGF stimulation and in tumours with MET overexpression in the presence of HGF-stimulated cell proliferation. Nonclinical studies have demonstrated the combination effect of savolitinib plus osimertinib, and this alongside clinical evidence has shown that the EGFR should still be inhibited in combination with MET inhibition to overcome resistance to EGFR-TKI and maintain remission.

In a subset of MET-driven EGFR TKI-refractory cancers, low EGFR:MET expression appears to predict MET dependence (ie, EGFR independence) in patient-derived xenograft models, suggesting a subset of patients with EGFR-mutant, MET-driven lung cancers may develop dependence on MET activation alone and may be treated with a single-agent MET-TKI.

This Phase II study (SAVANNAH) will investigate the efficacy and safety of osimertinib (80 mg od) in combination with savolitinib (300 mg od, 300 mg bid or 600 mg od) in patients with EGFRm+ and MET-amplified/overexpressed (patients with FISH10+ and/or IHC90+ status across all clinical study protocol (CSP) versions and patients with FISH5+ and/or IHC50+ status prior to CSP version 7.0), locally advanced or metastatic NSCLC who have progressed following treatment with osimertinib. The study will also investigate the difference in efficacy of savolitinib in combination with osimertinib and savolitinib monotherapy in the population enrolled under CSP version 7.0 with MET-amplified/overexpressed (FISH10+ and/or IHC90+) status who have progressed following treatment with 1L osimertinib therapy.

Objectives and Endpoints

Primary Objective:	Endpoint:

• To determine the efficacy of savolitinib (300 mg bid) in combination with osimertinib in patients with EGFRm+ and MET amplified/overexpressed (FISH10+ and/or IHC90+)^a, locally advanced or metastatic NSCLC who have progressed following treatment with 1L osimertinib• To determine the efficacy of savolitinib (300 mg od) in combination with osimertinib in patients with EGFRm+, MET amplified/overexpressed (FISH5+ and/or IHC50+)^b, locally advanced or metastatic NSCLC who have progressed following osimertinib.	
• ORR by investigator assessment in accordance with RECIST 1.1.
Secondary Objectives:	Endpoints:
To determine the efficacy of savolitinib (300 mg bid) in combination with osimertinib in patients with EGFRm+ and MET amplified/overexpressed (FISH10+ and/or IHC90+) ^a , locally advanced or metastatic NSCLC who have progressed following treatment with 1L osimertinib.	
• DoR and PFS by investigator assessment in accordance with RECIST 1.1• OS
To describe the difference in the efficacy of savolitinib (300 mg bid) in combination with osimertinib and savolitinib (300 mg bid) in combination with placebo in patients with EGFRm+, MET amplified/overexpressed (FISH10+ and/or IHC90+) ^a , locally advanced or metastatic NSCLC who have progressed following treatment with 1L osimertinib therapy under CSP version 7.0.	
• ORR by investigator assessment in accordance with RECIST 1.1

To determine the efficacy of savolitinib (300 mg od and 600 mg od, respectively) in combination with osimertinib in patients with EGFRm+, MET-amplified/overexpressed (FISH10+ and/or IHC90+)^a, locally advanced or metastatic NSCLC who have progressed following treatment with 1L osimertinib.
	
 • ORR, DoR, and PFS, by investigator assessment in accordance with RECIST 1.1. • OS

To determine the efficacy of savolitinib (300 mg od, 300 mg bid, and 600 mg od, respectively) in combination with osimertinib in patients with EGFRm+, MET-amplified/overexpressed (FISH10+ and/or IHC90+)^a, locally advanced or metastatic NSCLC who have progressed following treatment of ≥ 2L osimertinib.
	
 • ORR, DoR, and PFS, by investigator assessment in accordance with RECIST 1.1. • OS

To determine the efficacy of savolitinib (300 mg od, 300 mg bid, and 600 mg od, respectively) in combination with osimertinib in patients with EGFRm+, MET-amplified/overexpressed (FISH5+ and/or IHC50+)^b, locally advanced or metastatic NSCLC who have progressed following osimertinib.
	
 • ORR (except 300 mg od), DoR, and PFS by investigator assessment in accordance with RECIST 1.1. • OS

To determine the efficacy of (1) 300 mg od, 300 mg bid and 600 mg od of savolitinib in combination with osimertinib in patients with EGFRm+ MET amplified/overexpressed (FISH 10+ and/or IHC90+)^{a,b}; (2) 300 mg od, 300 mg bid and 600 mg od of savolitinib in combination with osimertinib in patients with EGFRm+ MET amplified/overexpressed (FISH5+ and/or IHC50+)^b (3) savolitinib 300 mg bid in combination with osimertinib and savolitinib 300 mg bid in combination with placebo, respectively, in patients with EGFRm+ MET amplified/overexpressed (FISH10+ and/or IHC90+)^a following treatment with 1L osimertinib.
	
 • ORR, DoR, and PFS assessed by BICR in accordance with RECIST 1.1

To assess the impact of savolitinib and osimertinib on disease-related symptoms and HRQoL in this patient population.
	
 • Mean change from baseline in EORTC QLQ-C30 and QLQ-LC13.

To evaluate the pharmacokinetics of osimertinib and savolitinib in this patient population.
	
 • Plasma concentrations of osimertinib, savolitinib and their metabolites.

To determine the prevalence of ctDNA clearance after osimertinib and savolitinib treatment in this patient population.
	
 • Total clearance in EGFR mutations at 6-weeks after therapy initiation (percentage and absolute change from baseline in EGFR mutation allele frequencies).

Safety Objectives:	Endpoints:
To evaluate the safety and tolerability of savolitinib in combination with osimertinib and savolitinib in combination with placebo.	
• AEs, SAEs and discontinuation rate due to AEs.• Clinical chemistry/haematology including LFTs.• ECHOs, ECGs and vital signs including blood pressure and heart rate.

^a Patients with MET-amplified/overexpressed NSCLC with FISH10+ (≥ 10 MET gene copies according to central MET FISH test) and/or IHC90+ ($\geq 90\%$ of tumour cells staining at strong 3+ intensity according to central MET IHC test).

^b Patients with MET-amplified/overexpressed NSCLC with FISH5+ (≥ 5 MET gene copies or MET:CEP7 ratio ≥ 2) and/or IHC50+ ($\geq 50\%$ of tumour cells staining at strong 3+ intensity).

Osimertinib 80 mg od is administered in the combination dosing regimens.

1L First line; 2L Second line; AE Adverse event; bid twice daily; BICR Blinded independent central review; CTCAE Common Terminology Criteria for Adverse Events; DoR Duration of response; ECG

Electrocardiogram; ECHO Echocardiogram; EGFR Epidermal growth factor receptor; EGFRm+ Epidermal growth factor receptor mutation positive; EQ-5D-5L EuroQol 5 dimensions, 5 levels; FACT-L Functional Assessment of Cancer Therapy - Lung Cancer; FISH Fluorescence in situ hybridisation; HRQoL Health-related quality of life; IHC Immunohistochemistry; LFT liver function test; MET Mesenchymal epithelial transition factor; MET/CEP7 Mean MET per cell and chromosome 7 centromere ratio; NGS Next generation sequencing; NSCLC Non-Small Cell Lung Cancer; od once daily; ORR Objective response rate; OS Overall survival; PFS Progression-free survival; PRO Patient reported outcomes; QLQ-LC13 Quality of Life Questionnaire-Lung Cancer 13; RNA Ribonucleic acid; SAE Serious adverse events.

Overall design:

This is a Phase II study to investigate the efficacy of osimertinib administered orally with savolitinib in patients with EGFRm+ and MET-amplified/overexpressed, locally advanced or metastatic NSCLC who have progressed following treatment with osimertinib.

Under CSP version 7.0, the SAVANNAH study will be expanded to further investigate the efficacy of savolitinib 300 mg bid + osimertinib in MET-amplified/overexpressed (FISH10+ and/or IHC90+) patients who have progressed following 1L osimertinib treatment. Per CSP version 7.0, the study will also describe the difference in the efficacy of osimertinib in combination with savolitinib 300 mg bid and savolitinib monotherapy in the treatment of EGFRm+ NSCLC patients with MET FISH10+ and/or IHC90+ status whose tumour has progressed following 1L osimertinib treatment.

The study design for patients who were enrolled under CSP versions 1.0 to 6.0, and for patients who will be enrolled under CSP version 7.0 is summarised in [Figure 1](#).

Study Period:

- Estimated date of first patient enrolled: Q4 2018
- Estimated date of last patient completed (final data cut-off): Q1 2025

Patient Population:

Prior to CSP version 7.0, eligible patients were those with histologically or cytologically confirmed diagnosis of EGFRm+, MET-amplified/overexpressed (FISH5+ and/or IHC50+) NSCLC that is locally advanced or metastatic and is not amenable to further surgery or radiotherapy with curative intent. The disease must have progressed following treatment with osimertinib.

Under CSP version 7.0, eligible patients will be those with histologically or cytologically confirmed diagnosis of EGFRm+, MET-amplified/overexpressed (FISH10+ and/or IHC90+) NSCLC that is locally advanced or metastatic and is not amenable to further surgery or radiotherapy with curative intent. The disease must have progressed following treatment with first-line osimertinib.

Number of Patients and intervention groups:

The study has a total of 4 dosing combinations:

- Osimertinib (80 mg od) + savolitinib (**300 mg od**) (explored under CSP versions 1.0 to 4.0)
- Osimertinib (80 mg od) + savolitinib (**300 mg bid**) (explored under CSP versions 5.0 to 7.0)
- Osimertinib (80 mg od) + savolitinib (**600 mg od**) (explored under CSP versions 1.0 to 2.0 and reintroduced under CSP versions 5.0 to 6.0)
- Placebo to osimertinib + savolitinib (**300 mg bid**) (explored under CSP version 7.0)

Overall, approximately **CCI** patients are planned to be treated in the study, including approximately **CCI** patients who will receive osimertinib (80 mg od) in combination with either savolitinib 300 mg od (n=**CCI** patients, approximately), savolitinib 300 mg bid (n=**CCI** patients, approximately), or savolitinib 600 mg od (n=**CCI** patients, approximately), and approximately **CCI** patients who will receive placebo to osimertinib + savolitinib 300 mg bid (with the opportunity to cross over to combination treatment on disease progression).

Under CSP version 7.0, approximately **CCI** patients with MET-amplified/overexpressed (FISH10+ and/or IHC90+) status who have progressed following treatment with 1L osimertinib will be randomised in a 2:1 ratio to receive savolitinib 300 mg bid + osimertinib 80 mg od (approximately **CCI** patients) or savolitinib 300 mg bid + placebo (approximately **CCI** patients) in a double-blind manner. Randomisation will be stratified according to the presence of brain metastases at baseline (yes versus no). At the time of investigator assessment of progressive disease (PD) per RECIST 1.1, the treatment group will be unblinded and patients who were initially randomised to the savolitinib 300 mg bid + placebo arm will be given the opportunity to cross over to the savolitinib 300 mg bid + osimertinib

80 mg od arm. Under CSP version 7.0, patients must have confirmation of MET-amplified/overexpressed (FISH10+ and/or IHC90+) tumour status by FISH (central) and IHC (central) testing. Pre-existing next generation sequencing testing results are not accepted to enter Screening.

Intervention duration

All patients confirmed as eligible will begin treatment on Day 1 with osimertinib + savolitinib combination therapy or placebo to osimertinib + savolitinib. Treatment will continue in 28-day cycles until either objective disease progression by investigator per RECIST 1.1 is assessed, unacceptable toxicity occurs, consent is withdrawn or another discontinuation criterion is met.

Patients randomised to the placebo + savolitinib 300 mg bid arm may cross over to osimertinib 80 mg od + savolitinib 300 mg bid following investigator-assessed PD per RECIST 1.1.

Independent data monitoring committees

An independent data monitoring committee will meet to assess the futility of the savolitinib 300 mg bid + placebo arm after **CC1** patients have been randomised under CSP version 7.0 and have had an opportunity to have 2 post-baseline scans. The IDMC will also review at this time the safety data of the randomised patients recruited under CSP version 7.0 for both arms (Appendix A 5). More details are provided in the IDMC charter.

In addition, **CC1**

Statistical considerations:

The study will have 5 planned analyses. Interim Analysis 1 was planned and performed after approximately **CC1** patients treated with osimertinib and 300 mg od savolitinib had the opportunity to be treated for 2 post-baseline Response Evaluation Criteria in Solid Tumour (RECIST) scans (12 weeks) or the **CC1** patient treated with osimertinib (80 mg od) and savolitinib (300 mg od) had the opportunity to be treated for 6 weeks, whichever was later. Continuous monitoring of the discontinuation due to adverse event (AE) rate and the discontinuation due to a hypersensitivity/anaphylaxis AE rate was to be performed after the **CC1** patient treated with osimertinib and 300 mg od savolitinib had the opportunity to be treated for 6 weeks up to the first interim analysis.

Interim Analysis 2 was planned and performed after approximately CC1 patients treated with osimertinib (80 mg od) and savolitinib (300 mg od) in the second line setting had the opportunity to be treated for 2 post-baseline scans (12 weeks).

The third planned analysis is a futility analysis for the placebo + savolitinib arm that is planned after CC1 patients have been randomised under CSP version 7.0 and have had an opportunity to have 2 post-baseline scans.

The primary (ORR) analysis for the study will be performed at CC1 months after the last patient under CSP version 7.0 has been randomised to treatment. The final analysis for the study will be performed at CC1 months after the last patient under CSP version 7.0 has been randomised to treatment.

Additional analysis for patients enrolled prior to CSP version 7.0 may be performed, if required.

Analyses will be performed by AstraZeneca or its representatives. A comprehensive Statistical Analysis Plan will be developed and will describe the patient populations to be included in the analyses, and procedures for accounting for missing, unused and spurious data. Any deviations from this plan will be reported in the clinical study report.

The analysis of objective response rate will be based on investigator assessment of RECIST 1.1 assessments. Objective response rate will be defined as a visit response of complete response (CR) or partial response (PR) which must be confirmed by a later scan conducted at least 4 weeks after the initial response is observed.

[figure not shown]
The efficacy endpoints will be summarised on the following datasets:

- Target Population Analysis Set (TPAS), defined as all patients assigned to savolitinib 300 mg bid + osimertinib who have FISH10+ and/or IHC90+ status, have progressed following 1L osimertinib and have taken ≥ 1 dose of either drug (primary endpoint population).
- Contribution of Components Analysis Set (CAS), defined as all patients randomised under CSP version 7.0 with treatment groups assigned in accordance with the randomisation, regardless of the treatment actually received.
- Safety Analysis Set (SAF), defined as all enrolled patients who take ≥ 1 dose of either study drug. The SAF will be used for reporting the efficacy of savolitinib 300 mg od + osimertinib in FISH5+ and/or IHC50+ patients (primary endpoint population). The SAF will also be used as the population for reporting the efficacy for patients dosed prior to CSP version 7.0.

Safety data will be summarised on the SAF. See the statistical analysis plan for further details. The general study design is summarised in [Figure 1](#).

